#### 9.1.2 Hb in the Primary Efficacy Period

Hb for the PEP will be calculated as the average of all Hb measurements from the central laboratory within the four visit windows during Weeks 24 through 36, regardless of intercurrent events. At least 1 Hb measurement is required for the calculation; otherwise, the value will be missing and therefore imputed. The PEP corresponds to Visits 10 through 13, also called analysis time period 3 ([Table 1](#)).

### 9.1.3 Change in Hb From Baseline to the Primary Efficacy Period

The change from baseline will be calculated for each subject as the PEP value minus the baseline value.

### 9.1.4 Analysis of Change From Baseline in Hb to the Primary Efficacy Period

The primary analysis will be performed in the randomized population, as defined in [Section 3.1](#), to address an estimand of treatment policy in accordance with the Intention to Treat philosophy. In this open-label study, the research question is to compare the assignment of a standard of care, darbepoetin, to the investigational new drug, vadadustat, regardless of intercurrent events. This analysis includes individuals who never receive treatment, discontinue treatment, are rescued with any therapy, or withdraw consent.

The primary analysis will use multiple imputation with ANCOVA as the substantive model. Missing primary endpoint data will be imputed with the group to which the subject was randomized as described in [Appendix B](#). An ANCOVA model, as described in detail in [Appendix C](#), will be used to compare the mean change from baseline in Hb between the 2 groups.

The primary analysis model will contain treatment group, baseline Hb level, and the 2 stratification factors (region and NYHA CHF class) as predictor variables. The stratification factor of entry Hb level will not be included in the model because of the inclusion of baseline Hb. The stratification factor assignments at randomization will be respected in the analysis.

The random seeds for all the multiple imputation runs for each trial will be generated from a single master seed. The master seeds will be 10014 for CI-0014, and 10015 for CI-0015. The generation code, resulting random seeds, and corresponding analysis assignments are listed in [Appendix B](#).

The data will have shown noninferiority of vadadustat if the lower bound of the 95% confidence interval for the difference in estimated change from baseline in the 2 groups (vadadustat minus darbepoetin) exceeds the noninferiority margin of -0.75. This ensures a 1-sided alpha of 0.025 for the primary analysis. If the lower limit of the 2-sided 95% confidence interval for the difference between the mean in the vadadustat group and the mean in the darbepoetin alfa group is above zero, superiority will have been established and the finding will be interpreted as providing evidence of a greater change from baseline in Hb for vadadustat relative to the control arm.

### 9.1.5 Sensitivity Analyses to the Primary Efficacy Results

To assess the robustness of the findings from the primary analysis, the following set of sensitivity analyses will be performed using a method analogous to that of the primary analysis (including multiple imputation) unless otherwise specified:

- The primary analysis will be repeated after setting to missing all per-visit Hb values within four weeks of administration rescue therapy or after EOT visits. The definition of rescue therapy will vary across the series described in [Section 6.3.9](#).
- Tipping point analyses (see [Appendix Section B.3.2](#)) will be performed to assess the effect of the missing data.

Statistical Analysis Plan AKB-6548-CI-0014 and AKB-6548-CI-0015

- The FAS population will be used instead of the randomized population without a new multiple imputation. This analysis will be performed only if the size of the FAS is less than 95% of the randomized population.
- The PP population with the actual treatment received without imputation
- A mixed model for repeated measures (MMRM) will be fit to the observed data only *without imputing missing values*. The repeated measures will be the observed averages for analysis time periods 1, 2, and 3 (See definitions in [Section 5.1](#) and analysis details in [Appendix C](#)).

## 9.2 Secondary Efficacy Endpoints: Definitions and Analyses

The study has one secondary efficacy endpoint which will be analyzed formally only if the primary analysis meets the noninferiority margin.

- Change in average Hb value between Baseline and the SEP (Weeks 40 to 52)

Evaluation of the average change in Hb will employ the approach described for the primary endpoint (see [Section 2.7](#) and [Section 9.1](#)) assessing Weeks 40 to 52 instead of Weeks 24 to 36. The power for this endpoint for a noninferiority margin of -0.75 g/dL is expected to be close to the power of the primary endpoint.

Sensitivity analyses analogous to those performed for the primary efficacy endpoint will be repeated to assess mean change in Hb from Baseline to Weeks 40 to 52. For ANCOVA models, analysis time period 4 will replace 3, and for MMRM, the models will be extended to include four post-baseline timepoints.

## 9.3 Other Efficacy Endpoints: Strategies for Analysis

The study has many other efficacy endpoints. Because of their exploratory nature, they will not be corrected for multiplicity.

### 9.3.1 Having Average Hb Value in the Geography-Specific Target Range in Weeks 24 to 36

All subjects will be defined as either being in their geography-specific target range (see [Section 2.3](#)) in Weeks 24 through 36 (“yes”) or not (“no”), based on the average Hb value during the four visit windows in Weeks 24 through 36. Subjects with no Hb value in the PEP value will be treated as missing and handled according to [Appendix B](#).

The proportion of subjects within target range will be calculated and tested with a Mantel-Haenszel test stratified by the baseline strata. See [Appendix B](#) and [Appendix D](#).

Noninferiority will be evaluated using a 2-sided confidence interval for the difference in proportions. Noninferiority will have been established if the lower limit of the confidence interval is above -15%. The power for this endpoint is expected to be roughly 90%.

If the lower limit of the 2-sided confidence interval for the difference in proportions is above zero, superiority will have been established and the finding will be interpreted as providing evidence of a higher proportion of subjects being within the target range for vadadustat relative to the control arm.

### 9.3.2 Having Average Hb Value in the Geography-specific Target Range in Weeks 40 to 52

All subjects will be defined as either being in their geography-specific target range (see [Section 2.3](#)) in Weeks 40 to 52 (“yes”) or not (“no”), based on the average Hb value during the Weeks 40 to 52 visit windows. Subjects with no Hb value in the SEP value will be treated as missing and handled according to [Appendix B](#).

The proportion of subjects within target range will be calculated and tested with a Mantel-Haenszel test stratified by the baseline strata. See [Appendix D](#).

Noninferiority will be evaluated using a 2-sided confidence interval for the difference in proportions. Noninferiority will have been established if the lower limit of the confidence interval is above -15%. The power for this endpoint is expected to be roughly 90%.

If the lower limit of the 2-sided confidence interval for the difference in proportions is above zero, superiority will have been established and the finding will be interpreted as providing evidence of a higher proportion of subjects being within the target range for vadadustat relative to the control arm.

[Table 3](#) lists the other efficacy endpoints. All analyses will stratify by the randomization (baseline) strata.

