5.3 Secondary Efficacy Endpoints

The key secondary efficacy endpoints include the following:

- Mean change in Hb value between Baseline (mean pretreatment Hb) and the secondary evaluation period (Weeks 40-52)
- Proportion of subjects with Hb values within the target range during the primary evaluation period (Weeks 24-36)
- Proportion of subjects with Hb values within the target range during the secondary evaluation period (Weeks 40-52)

Other secondary efficacy endpoints include:

- Proportion of time with Hb values within the target range during the primary evaluation period (Weeks 24-36)
- Proportion of time with Hb values within the target range during the secondary evaluation period (Weeks 40-52)
- Proportion of subjects with Hb increase of >1.0 g/dL from Baseline

- Time to achieve Hb increase of >1.0 g/dL from Baseline
- Mean change in Hb between Baseline (mean pretreatment Hb) and the primary evaluation period (mean Hb from Weeks 24-36) stratified by pre-baseline ESA exposure
- Progression of CKD
- Proportion of subjects receiving IV iron therapy from Baseline visit to Week 52
- Mean monthly dose of IV elemental iron administered from Baseline to Week 52 in subjects who have received IV iron
- Proportion of subjects receiving RBC transfusion(s) from Baseline to Week 52
- ESA rescue
- Dose adjustments from Baseline to Week 52
-

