## APPENDIX D. ANALYSIS OF NON-NORMAL ENDPOINTS

### D.1. Analysis of Binary Endpoints

This section describes the methods for analyzing other binary endpoints.

For each binary endpoint, a 95% confidence interval will be calculated for each proportion by treatment group using the Clopper-Pearson method [Clopper, 1934].

For analyses conducted in the randomized population, the weighted difference in proportions between treatment groups, adjusting for the stratification factors, and the corresponding 2-sided 95% confidence interval will be calculated by weighting according to the Mantel-Haenszel method. The associated odds ratio and corresponding 2-sided 95% confidence interval will also be calculated. Subgroup analysis will be conducted similarly.

The below efficacy endpoints have binary outcome measures and will use the code structure presented in [Exhibit D 1](#). For the first 4 endpoint, noninferiority will have been established if the lower limit of the confidence interval for the risk difference is above -15%.

- At least 1 Hb value in the geography-specific target range in Weeks 24 to 36
- At least 1 Hb value in the geography-specific target range in Weeks 40 to 52
- Hb values in the geography-specific target range for at least 1/2 of the observations in Weeks 24 to 36
- Hb values in the geography-specific target range for at least 1/2 of the observations in Weeks 40 to 52
- Hb increase of >1.0 g/dL in Year 1 (CI-0014)
- Receipt of at least 1 administration of elemental iron, repeated using each route, intravenous (IV), or oral
- Receipt of any red blood cell (RBC) transfusion
- Receipt of any erythropoietin-stimulating agent (ESA) rescue medication
- Receipt of any rescue therapy (series of definitions from narrow to broad)
- Hb values >12, 13, or 14 g/dL
- Hb values <8 or 9 g/dL
- Hb increase of >1.0 g/dL within any 2-week period (CI-0015)
- Hb increase of >2.0 g/dL within any four-week period (CI-0015)

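### The SAP calls the target-range proportions exploratory and uncorrected, yet sets rules under which noninferiority and superiority on them are established, with no gate or order

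*SAP*

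**What the plan says.** SAP 9.3 introduces the other efficacy endpoints with the statement "Because of their exploratory nature, they will not be corrected for multiplicity". Its first two subsections cover the proportion of subjects whose average Hb lies in the regional target range, at Weeks 24-36 (9.3.1) and Weeks 40-52 (9.3.2). Each subsection contains:

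- a noninferiority rule with a 15-point margin: "Noninferiority will have been established if the lower limit of the confidence interval is above -15" per cent;
- a power statement: "The power for this endpoint is expected to be roughly 90" per cent;
- a superiority rule: "If the lower limit of the 2-sided confidence interval for the difference in proportions is above zero, superiority will have been established".

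Appendix D.1 lists four alternative target-range definitions (at least one value in range, and at least half of the values in range, in each period). For these, "noninferiority will have been established if the lower limit of the confidence interval for the risk difference is above -15" per cent.

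The only gate is in SAP 9.2. It makes the formal analysis of a single endpoint, Hb change to Weeks 40-52, depend on the primary meeting its margin. C.1.3 declares the remaining analyses descriptive, but only for continuous endpoints, so it does not reach these proportions. The error statement in 9.1.4 is confined to the primary: "This ensures a 1-sided alpha of 0.025 for the primary analysis".

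The amended protocol ranks the two proportions differently. Its key secondary list in 5.3 includes "Proportion of subjects with Hb values within the target range during the primary evaluation period (Weeks 24-36") and the matching item for Weeks 40-52.

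**The concern.** An endpoint cannot be exploratory and uncorrected and also be the basis of a claim that is established. A team that follows 9.3 literally could report that "superiority will have been established and the finding will be interpreted as providing evidence of a higher proportion of subjects" is in range on vadadustat, without error control across the claims and whatever the primary showed. The protocol names these proportions as key secondary endpoints, so readers are likely to treat such a statement as confirmatory. The SAP does not explain the change of status. The MACE SAP (4.5) does set a hierarchy, gated on its primary, for its secondary endpoints. The efficacy SAP has nothing equivalent for these two.

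**Working it through.** **Inputs from the documents.** 925 subjects per arm (SAP 2.6), 1:1 allocation (2.1), margin 15 points (9.3.1, 9.3.2, D.1), stated power roughly 90% for each proportion. Section 9.3 gives no confidence level. D.1 uses two-sided 95%, so each claim is taken at one-sided 0.025 (z = 1.960).

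**Assumed, because the documents are silent.** Equal in-range proportions p in both arms, from 30% to 70%. Correlation between the two range statistics 0.4 to 0.6.

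**1. The SAP's own power figure.** Power = Φ(0.15/SE − 1.960), with SE = √(2p(1−p)/925).

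- p = 50% (worst case): SE = 0.02325; 0.15/0.02325 = 6.452; 6.452 − 1.960 = 4.492; power 99.9996%. At 30% or 70% it is higher.
- With 555 informative subjects per arm (60%): SE = 0.0300; 4.997 − 1.960 = 3.037; power 99.88%.
- 90% power at p = 50% needs (1.960 + 1.282)² × 2 × 0.25/0.15² = 233.5, so 234 per arm. At 30% or 70% it needs 197.
- At 925 per arm and a 50% control rate, 90% corresponds to a true deficit of about 7.5 points.

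The stated figure is therefore not reproduced at equality, and the SAP states no assumption that would give it.

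**2. False superiority statements with no true difference.** For the two proportions, P(at least one) = 1 − Φ₂(1.960, 1.960; ρ), where Φ₂ is the bivariate normal distribution function.

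| ρ | two range statements | plus the primary's statement |
|---|---|---|
| 0.4 | 4.66% | 1 − 0.975 × 0.9534 = 7.0% |
| 0.6 | 4.38% | 1 − 0.975 × 0.9562 = 6.8% |

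The last column treats Hb change and range as independent. If they are positively correlated (0.3 to 0.5), simulation of the three statistics gives 6.1-6.8%.

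**3. What a gate on the primary would do.** With no true difference and the planned SD of 1.5 g/dL, SE = 1.5 × √(2/925) = 0.0697, and 0.75/0.0697 − 1.960 = 8.8. Primary noninferiority then passes almost always, so a gate on it alone leaves the 4.4-4.7% nearly unchanged. Ordering the two superiority claims is what brings the error back to 2.5%.

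**4. Cost of a fixed sequence.** Each step keeps the full one-sided 0.025.

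- Noninferiority, equal arms at 50%: both range steps pass with probability 0.9999965² = 99.9993%, taking them as independent.
- Noninferiority, 50% against 43%: SE = √((0.25 + 0.2451)/925) = 0.02314; 0.08/0.02314 − 1.960 = 1.498; 93.3% for one step, and 0.933² = 87.0% for the second behind the first.
- If the SAP's 90% were right, the second step would fall to 81% (independent), 83% (ρ = 0.5) or 86% (ρ = 0.8).
- Superiority, 56.5% against 50%: SE = 0.02315; 0.065/0.02315 − 1.960 = 0.848; 80% alone, and about 69% behind the other range claim at ρ = 0.5.

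**The case against.** The SAP says in its introduction that its methods prevail over the protocol's, so it may reclassify these endpoints. The amended protocol's own section on key secondary analyses (11.6.2.1) gives a method only for Hb change at Weeks 40-52. Uncorrected exploratory endpoints are an acceptable choice, and noninferiority followed by superiority on one endpoint's confidence interval needs no extra alpha. All of this stands. It means the SAP need not promote the proportions. It does not reconcile the exploratory label with rules for established claims.

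A reader might infer more than the documents support:

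- **That four superiority statements give an error of 8-9%.** That count needs a superiority claim on Weeks 40-52 Hb change. SAP 9.2 supplies it only by referring to the primary's approach, and C.1.3 mentions noninferiority alone. It also treats Hb change and range as independent, although both derive from the same Hb averages.
- **That the figures measure the harm when the primary fails.** They assume equal arms, where the primary almost never fails. The missing gate is a defect in the text, and no size is attached to it here.
- **That a testing order is free.** This holds only for noninferiority near equality.
- **That the SAP breaks a protocol promise of hierarchical testing.** That sentence stands only in the original protocol (11.6.2), which has been superseded.

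**Conclusion.** The contradiction in SAP 9.3 and the lack of any gate or order are plain from the text, and D.1 extends the noninferiority rule to four more definitions. With no true difference, the error is about 4.4-4.7% for the two range superiority statements and about 7% with the primary's added, against 2.5% one-sided. The sizes rest on assumed correlations, and the 7% also on independence of Hb change and range. Positive dependence between those two would lower it somewhat.

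The primary noninferiority test and its 0.025 are untouched. What changes is which further claims the trial may make. The roughly 90% power given for these endpoints does not follow from 925 per arm, a 15-point margin and equal arms.

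**What to change.** Choose one of two repairs before database lock.

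**(a) Keep the endpoints exploratory.** In 9.3.1, 9.3.2 and D.1, replace the rules for establishing noninferiority and superiority with estimates and 95% confidence intervals described as descriptive. Say why the protocol's key secondary status was dropped. Cost: SAP text, and the uncontrolled claims are given up.

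**(b) Make the claims controlled.** Test in one fixed sequence at two-sided 5%, stopping at the first failure:

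1. Hb-change noninferiority, Weeks 24-36
2. Hb-change noninferiority, Weeks 40-52
3. target-range noninferiority, Weeks 24-36
4. target-range noninferiority, Weeks 40-52
5. every superiority claim to be kept, including those on Hb change, in a stated order.

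Make the D.1 definitions descriptive. Steps 1 and 2 are unchanged. Steps 3 and 4 lose almost nothing if the arms are equal. If vadadustat is truly 7 points worse, power at step 4 falls from about 93% to 87%. Later superiority claims also lose some power.

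Option (b) needs more than wording. Exhibit B 2 applies the range limits to the change scores DELT_HB3 and DELT_HB4 instead of the Hb level, so that code must be corrected. The endpoint definition should also be aligned, since the protocol refers to Hb values in range and SAP 9.3 to the average.

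Under either option, state the confidence level in 9.3. If a power figure is kept, give the in-range rates and true difference behind it.

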**Table 3. Other Efficacy Endpoints**

| Endpoint  | Approach to Analysis   | Comments   |
|---|--|--|
| Hb endpoints – Section 6.3.2  |  |  |
| Change in average Hb value between Baseline and the combined primary efficacy period (PEP) and secondary efficacy periods (SEP) (Weeks 24-52) | Analysis of covariance (ANCOVA) stratified by baseline strata. | Average may include imputed values for PEP and/or SEP.   |
| Having Hb values in the geography-specific target range during PEP or SEP (2 alternate definitions)   | Mantel-Haenszel test stratified by the baseline strata         | This analysis includes the observed hemoglobin values.   |
| CI-0014 only: Hb increase of >1.0 g/dL from Baseline to any time before Week 52   | Mantel-Haenszel test stratified by baseline strata             | This analysis includes the observed hemoglobin values.   |
| CI-0014 only: Time to achieve Hb increase of >1.0 g/dL from Baseline Hb (censored at Week 52)   | Time – to – event  | This analysis will use only observed data.   |
| Progression of CKD ( Section 6.3.6 )  |  |  |
| Progression of CKD (entire length of study)   | Time – to – event  |  |
| Iron endpoints ( Section 6.3.3 )  |  |  |
| Receipt of at least 1 administration of elemental iron ( IV, or oral)   | Mantel-Haenszel test stratified by baseline strata             |  |
| Average weekly dose of elemental iron, IV, or oral  | ANCOVA stratified by baseline strata.                          | If the distribution is highly skewed either because of a large spike at zero or a long tail to the right (or both), other methods may be considered. |

## Statistical Analysis Plan AKB-6548-CI-0014 and AKB-6548-CI-0015

| Endpoint   | Approach to Analysis  | Comments   |
|--|---|--|
| Hepcidin, Ferritin, TIBC   | Four outcomes – change from baseline to PEP, change from baseline to SEP, percentage change from baseline to PEP, and percentage change from baseline to SEP.

Analysis of covariance stratified by baseline strata for change from baseline to PEP or SEP. | This analysis will use only observed data  |
| Serum Iron   |   |  |
| TSAT   |   |  |
| Other laboratory endpoints ( Section 6.3.4 )                                 |   |  |
| Change from baseline in serum glucose and lipid parameters at PEP and SEP                    | ANCOVA stratified by baseline strata.   | No imputation.   |
| RBC transfusion endpoints ( Section 6.3.7 )                                  |   |  |
| Receipt of any RBC transfusion   | Mantel-Haenszel test stratified by the baseline strata  |  |
| Total number of RBC transfusions received (entire length of study)                           | See Appendix D .  | If the distribution is highly skewed either because of a large spike at zero or a long tail to the right (or both), other methods may be considered. |
| Dose adjustment ( Section 6.3.5 )  |   |  |
| Dose adjustments (entire length of study)  | Descriptive statistics  | Other methods may be considered.   |
| ESA and Rescue endpoints ( Section 6.3.8 and Section 6.3.9 ) |   |  |
| Receipt of any ESA rescue medication   | Mantel-Haenszel test stratified by the baseline strata  |  |
| Receipt of any rescue therapy (series of definitions from narrow to broad)                   | Mantel-Haenszel test stratified by the baseline strata  |  |

## 10 SAFETY ANALYSES

Unless otherwise specified, safety analyses will be performed using the safety population.

Most of the analysis of safety data will be descriptive without formal statistical testing. In some cases, 95% confidence intervals for the change from baseline as well as for the difference between the study groups may be reported.

Formal statistical methodology will be used for the MACE data; the methods are described in a separate SAP.

### 10.1 Mortality

The number and cause of death will be reported and summarized by treatment arm.

## 10.2 Hb-related Safety Endpoints

Hb-related safety endpoints will be defined using data from the central laboratory. The analyses will use all central laboratory values in the database starting from randomization. No imputation will be performed for missing data. For each endpoint in [Table 4](#), the proportion of the study group who satisfy the definition will be calculated stratified by the baseline strata. The 95% confidence intervals for these proportions will be reported along with the difference in proportions as well as the odds ratio; a Mantel-Haenszel weighting method will be used to calculate the 95% confidence intervals for these statistics (see [Appendix D](#)).

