8.4.7.2 Red Blood Cell Transfusion (Optional)

Investigators will use their local institution's transfusion guidelines when determining whether to transfuse a study subject. In general, in the event of an acute or severe loss of blood, a RBC transfusion should be administered as clinically indicated. In less severe instances but where there may be worsening of anemia or moderate to severe symptoms of anemia, RBC transfusions are permitted at the discretion of the Investigator given the medical necessity. Reasons for RBC transfusion will be captured in the appropriate CRF (e.g., worsening anemia due to CKD, blood loss, surgery, etc.). Study medication (vadadustat or darbepoetin alfa) may be continued during the RBC transfusion period.

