### *Study CI-0015*

- Conversion and Maintenance Period (Weeks 0-52):
  - Weeks 0 to 23: conversion to study treatment for maintaining Hb
  - Weeks 24 to 36: PEP
  - Weeks 40 to 52: SEP

After Week 52, subjects in both studies will proceed to the following 2 periods:

- **Long-Term Treatment Period (Weeks 53-End of Treatment [EOT]):** continued treatment with study medication to assess long-term safety
- **Follow-up Period (EOT + 4 weeks):** post-treatment visit (either in person or by telephone) to assess safety

The duration of the trial will depend on how long it takes for a total of 631 adjudicated MACE to occur in the 2 studies combined. A separate SAP will describe the planned MACE analyses, including the method planned for pooling data from the 2 PRO2TECT studies.

The safety reporting period for a subject enrolled in this study begins upon randomization and ends at the final protocol-required study contact (visit or telephone), also known as a subject's end of study (EOS). In addition, the Investigator should report any adverse event (AE) that occurs after this period if he or she assesses it as possibly or probably related to the study medication.

According to the schedule of visits in the protocol, no laboratory assessments, physical exams, or other procedures are planned after the subject's permanent discontinuation of study medication, also known as EOT; however, AE and rescue therapy assessments, including monitoring for MACE endpoints, will continue until a subject's EOS.

The analysis time periods for efficacy divide the Correction/Conversion and Maintenance periods, Year 1 collectively, into four windows (see [Table 1](#)).

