**Table 4. Hb-related Safety Endpoints from First Dose Date to Last Visit**

| Variable   | Criterion for "yes"   |
|--|---|
| Hb >12.0 g/dL                                    | Any Hb >12.0 g/dL after Day 1   |
| Hb >13.0 g/dL                                    | Any Hb >13.0 g/dL after Day 1   |
| Hb >14.0 g/dL                                    | Any Hb >14.0 g/dL after Day 1   |
| Hb increase >1.0 g/dL within any 2-week interval | Difference between 2 Hb values within any 2 weeks >1.0 g/dL after Day 1 |
| Hb increase >2.0 g/dL within any 4-week interval | Difference between 2 Hb values within any 4 weeks >2.0 g/dL after Day 1 |
| Hb <9.0 g/dL                                     | Any Hb <9.0 g/dL after Day 1  |
| Hb <8.0 g/dL                                     | Any Hb <8.0 g/dL after Day 1  |

Hb: hemoglobin

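### The Hb safety endpoints are reported only as ever/never proportions, so unequal time under central Hb observation can by itself separate the arms in the threshold rows

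*SAP*

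**What the plan says.** SAP 10.2 defines the Hb safety endpoints from central laboratory data: "The analyses will use all central laboratory values in the database starting from randomization". The summary measure is that "the proportion of the study group who satisfy the definition will be calculated stratified by the baseline strata", reported with a difference, an odds ratio and 95% confidence intervals under Mantel-Haenszel weighting. The title of Table 4 sets the window: "Hb-related Safety Endpoints from First Dose Date to Last Visit". A threshold row is met by a single value, for example "Any Hb >12.0 g/dL after Day 1". A rapid-rise row is met by any qualifying pair: "Difference between 2 Hb values within any 2 weeks >1.0 g/dL after Day 1". Appendix D.1 lists these endpoints as binary. Appendix D.3, on time to event, does not list them.

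On how long Hb is observed, SAP 2.2 states that "no laboratory assessments, physical exams, or other procedures are planned after" permanent discontinuation of study drug. The amended protocol (Amendment 7-COL) places the EOT visit at discontinuation and makes later follow-up flexible, centred on status, MACE and adverse events. Section 11.5 of the same protocol says instead that subjects who stop drug should carry on with planned visits and assessments.

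On rescue, protocol 8.4.7.2 says study drug "may be continued during the RBC transfusion period", and 8.4.7.1 allows ESA rescue from Week 6. SAP 10.2 has no rule for Hb values that follow either. A sensitivity analysis of the primary endpoint in SAP 9.1.5 does have one: "setting to missing all per-visit Hb values within four weeks of administration rescue therapy".

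**The concern.** An ever/never proportion is comparable between arms only if the arms are watched for similar lengths of time. Here the planned watching ends with study drug, treatment is open-label, and nothing in the design equalises time on drug. The arm that stops earlier has fewer draws on which an excursion can be seen.

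The stake is interpretation, not type I error. SAP 7 says the arms will be compared on these endpoints, and protocol 4.3 links Hb oscillations and overshoots to adverse cardiovascular outcomes. A difference and odds ratio with confidence intervals will be read as a treatment effect on excursions, even though SAP 10 calls most safety analysis descriptive.

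A second, smaller issue is confined to the rapid-rise rows. A rise between two draws counts whatever produced it, including a transfusion or ESA rescue given in between.

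**Working it through.** The documents give no excursion rate, stopping rate or power for these endpoints, so there is no figure of the plan's to reproduce. From the documents come the ever/never definition, 925 subjects per arm (SAP 2.6), an expected mean follow-up of about 2 years (MACE SAP 2.5.1) and the visit schedule (protocol 9). All rates below are assumptions.

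**Threshold rows, fixed observation time.** With a constant true rate r, equal in both arms, and observation time t, P(ever) = 1 − exp(−r·t).

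- r = 0.10 per year, t = 1.7 v 1.3 years: 1 − e^(−0.17) = 15.6% and 1 − e^(−0.13) = 12.2%. Difference −3.4 points, ratio 0.78.
- r = 0.20 per year, same times: 28.8% v 22.9%, difference −5.9 points.

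**Threshold rows, stopping as a process.** With stopping rate d, horizon T = 2 years and observation ending at stopping, P(ever) = r/(r+d) × [1 − exp(−(r+d)T)].

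| r per year | d per year | P(ever) | Difference | Odds ratio | Chance 95% CI excludes 0 (925 per arm) |
|---|---|---|---|---|---|
| 0.1 | 0.2 v 0.4 | 15.0% v 12.6% | −2.4 | 0.82 | 32% |
| 0.3 | 0.2 v 0.3 | 37.9% v 34.9% | −3.0 | 0.88 | 27% |
| 0.3 | 0.2 v 0.4 | 37.9% v 32.3% | −5.6 | 0.78 | 72% |
| any of these | equal | equal | 0 | 1.00 | – |

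**Same scenario with person-time.** Mean time at risk is [1 − exp(−(r+d)T)]/(r+d). For r = 0.3 this is 0.632/0.5 = 1.264 years and 0.753/0.7 = 1.076 years. The rates are 0.379/1.264 = 0.30 and 0.323/1.076 = 0.30 per year, a ratio of 1.00. The artefact disappears, provided stopping is unrelated to excursion risk.

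**Rapid-rise rows.** Central draws are every 2 weeks from Week 2 to Week 12, every 4 weeks to Week 52, then 12 to 16 weeks apart. Scheduled post-Day-1 pairs two weeks apart are therefore 2–4, 4–6, 6–8, 8–10 and 10–12. The last scheduled four-week pair is 48–52. Time on drug beyond those points adds no scheduled pairs.

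For transfusion, assume 8% v 12% transfused, spread evenly over about 1.5 years (78 weeks), a true rise of 1.5 to 2.0 g/dL and a draw SD of 0.35, so the SD of a difference is 0.35√2 = 0.495.

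- Two-week row: share that can be bracketed 10/78 = 0.13; P(rise >1.0) = 0.84 to 0.98; spurious difference 4 × 0.13 × (0.84 to 0.98) = about 0.4 to 0.5 points.
- Four-week row: share 50/78 = 0.64; P(rise >2.0) = 0.16 to 0.50; 4 × 0.64 × (0.16 to 0.50) = about 0.4 to 1.3 points. This is on the high side, since the visit windows push some pairs past 28 days.

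**The case against.** The strongest case for leaving the plan alone has five parts.

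- **The proportion is the protocol's own specification** (11.7.3), and the outputs are largely descriptive. True, so the proportion should stay. That does not make it sufficient alone.
- **Imbalances are visible elsewhere.** Discontinuation and exposure (SAP 4.3), transfusion rates per person-year (6.3.7) and rescue incidence (6.3.9) are reported by arm. A careful reader could suspect an artefact from these but could not correct for it.
- **Observation may not end with drug.** Protocol 11.5 says visits and assessments should continue, and SAP 9.1.5 anticipates Hb values after EOT. This stands: a reader might take SAP 2.2 as settling the matter, and the documents do not allow that. If later values exist they are counted to the original arm, although subjects may by then be on standard-of-care ESA.
- **A constant detection rate flatters the effect.** After Week 52 Hb is sampled only every 12 to 16 weeks, so late exposure counts for less than the model assumes. This stands.
- **Censoring at the last Hb may be informative** if stopping depends on Hb response. This also stands, and is a reason to show both presentations.

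Three stronger readings are tempting. First, a reader might infer that rescue is read as overshoot throughout Table 4. The ESA criterion is Hb <9.0 g/dL (with investigator discretion) and rescue stops at ≥9.5, so it is unlikely to produce values above 12, 13 or 14; the <9 and <8 rows are not overshoot at all. Second, a reader might assume that transfusions usually fall between two qualifying draws. Beyond Week 12 (two-week row) or Week 52 (four-week row), the schedule supplies no such pairs. Third, SAP 9.1.5 might suggest that the plan regards post-rescue values as unusable for efficacy. The primary analysis keeps them regardless of intercurrent events (9.1.2, 9.1.4); only a sensitivity analysis removes them.

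**Conclusion.** The concern holds for the five threshold rows. With ever/never proportions as the only planned analysis and Hb observation tied to study drug under SAP 2.2, unequal stopping turns equal excursion rates into an apparent difference: 15.6% v 12.2% in the simple example. It runs from −1.3 to −14.4 points over assumed excursion rates of 0.1 to 0.6 per year and stopping rates of 0.2 v 0.3 to 0.6 per year. These figures rest wholly on assumed rates. It cannot be said in advance that the arm stopping sooner will look safer, because the documents do not show that either arm will stop sooner; with equal stopping the artefact is zero.

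For the two rapid-rise rows the issue is narrower: few scheduled pairs are eligible, subjects without one cannot score, and a modest number of rises may reflect transfusion or rescue. Earlier stopping lowers a proportion and more rescue raises it, so the two effects can also offset each other.

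**What to change.** In SAP 10.2:

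1. **Threshold rows.** Add first events per 100 patient-years of central Hb observation, and time to first event from first dose, with Kaplan-Meier curves and a stratified Cox hazard ratio with CI, censored at the last central Hb. Appendix D.3 already applies that censoring rule to laboratory time-to-event endpoints, and 6.3.7 already uses person-years for transfusion. Keep the protocol-specified proportions alongside.
2. **Rapid-rise rows.** Keep the all-values proportion, but limit the denominator to subjects with at least one eligible pair of draws. Add, as a sensitivity analysis only, a count excluding pairs that bracket a transfusion or ESA rescue. State next to it that the rescue definition differs by arm: under SAP 6.3.9 any ESA may count as rescue on vadadustat, whereas darbepoetin dose increases count only if the investigator designates them so. ESA-driven rises would otherwise be dropped in one arm and kept in the other without notice.
3. **Observation window.** Reconcile SAP 2.2 with protocol 11.5 on assessments after permanent discontinuation, and state whether post-EOT Hb values enter Table 4.

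The cost is SAP wording and a few tables, with no new data or visits. The limitation to declare is that censoring at the last Hb assumes stopping is unrelated to excursion risk.
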